APPENDIX 1 – TABLE WITH STUDY DEFINITIONS

Airway injury	Any detectable and clinically relevant injury attributable to tracheal intubation procedure (e.g bleeding, tracheal or bronchial tear or laceration)
Advanced airway management	The use of either a supraglottic airway device or tracheal intubation as airway management method to provide general anesthesia
Cannot Intubate Cannot Oxygenate Scenario (CICO)	Impossibility to achieve a successful tracheal intubation and adequate patient's oxygenation.
Cardiac arrest	Pulseless dysrhythmia occurring during/after advanced airway management
Cardiovascular collapse	 At least one of the following, occurring within 30 minutes from advanced airway management or up to surgical incision: SAP < 65 mmHg SAP < 90 mmHg for > 15 minutes or up to incision if it comes before 15 min Unplanned need of vasopressors and/or fluid load > 15 ml/kg to maintain the target blood pressure.
Early cardiovascular collapse	Any cardiovascular collapse event occurring up to 10 minutes from induction (or surgical incision, whichever come first)
Late cardiovascular collapse	Any cardiovascular collapse event occurring from 11 to 30 minutes from induction (or surgical incision, whichever come first)
Clinically relevant airways bleeding	Any sign or symptom of airways haemorrhage that meet at least one of the following criteria: • requiring medical intervention by a healthcare professional • leading to hospitalization or increased level of care • Prompting a face to face evaluation
Dental trauma	Fracture or avulsion of tooth during airway management

Difficult mask ventilation	Impossibility to provide adequate ventilation because of one or more of the following problems: inadequate mask seal, excessive gas leak, or excessive resistance to the ingress or egress of gas
Difficult tracheal intubation	Procedure requiring > 2 laryngoscopy attempts
Duration of the airway management procedure	Difference between time of confirmed airway device placement and preoxygenation start
Emergency front of neck access (eFONA)	Emergency need for invasive access to the patient's neck to provide adequate oxygenation (e.g. cricothyroidotomy, percutaneous tracheostomy, surgical tracheostomy).
Severe hypertension	Systolic arterial pressure > 180 mmHg
Attempt	Each time a device (SGA, laryngoscope, fiberscope) is introduced in patient's mouth/nose.
Moderate Hypoxia	SpO ₂ < 93%
Oral aspiration of gastric contents	Presence of vomit at the glottic inlet visualised during airway management in a previously clear airway
Rapid Sequence Induction- Intubation	Administration of rapid-onset induction agents and muscle relaxant with no ventilation between induction and laryngoscopy
Severe Hypoxia	SpO ₂ < 80%
Unplanned need of vasopressor	Rescue administration of any vasopressor (either as a bolus or continuous infusion) due to hypotension after induction

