The primary aim of the study is to assess the current incidence of major peri-intubation adverse events during anaesthesia in patients undergoing elective or emergency surgery and in the setting of nonoperating room anaesthesia. The secondary aim is to assess the current practice of airway management during anaesthesia worldwide.

STUDY DESIGN

International, multicenter, prospective cohort study.

POPULATION

Inclusion criteria

We will include all adult (≥ 18 years old) patients undergoing advanced airway management for general anaesthesia in operating room or non-operating room anaesthesia (NORA) locations. We will include all the procedures both diagnostic and therapeutic, elective, or emergency that will require an advanced airways management (either tracheal intubation or SGA placement).

All potentially eligible patients will be identified by local investigators by screening the OR schedule and the procedures performed outside the OR.

Exclusion criteria

We will exclude the airway management during cardiopulmonary resuscitation. Critical patients undergoing advanced airway management in ED, wards or ICU, due to their underlying clinical condition will not be included in the study.

PRIMARY OUTCOME

At least one of the following major adverse events occurring within 30 minutes from induction or up to surgical incision:

Major adverse event:

- Severe hypoxia (SpO₂ < 80%)
- Cardiovascular collapse (at least one of the following):
 - Systolic arterial pressure < 65 mmHg
 - Systolic arterial pressure < 90 mmHg for > 15 minutes
 - Unplanned need of vasopressors and/or fluid load > 15 ml/kg to maintain the target blood pressure.
- Cardiac arrest

Blood pressure values should be confirmed in two consecutive measurements on non-invasive blood pressure monitoring or for 10 seconds on invasive monitoring system.

SECONDARY OUTCOMES

- Minor adverse events:
 - Moderate hypoxia (SpO₂ < 93%)
 - Airway injury
 - Clinically relevant bleeding
 - Oral aspiration of gastric contents
 - Dental injury
- Difficult facemask ventilation
- First pass success rate
- Early cardiovascular collapse
- Late cardiovascular collapse

OTHER OUTCOMES

- Unplanned need for ICU admission secondary to airway management related complications
- Emergency front of neck airway (eFONA)
- Cannot intubate cannot oxygenate scenario (CICO)
- In-hospital mortality
- Post-procedural severe hypertension
- Difficult procedure (more than 2 attempts)

DATA COLLECTION

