Data will be collected real-time by an investigator not involved in airway management using either the paper or the electronic version of the case report form on the Redcap.

The following variables will be collected:

- Informed consent and admission data
- Demographic and clinical characteristics
- Type of procedure (time, setting, type of surgery, elective or emergency

- Airway evaluation (anticipated difficult airway management)
- Monitoring applied during the procedure
- Ongoing respiratory and hemodynamical support before intubation
- Patient's parameters
- Preoxygenation method and use of apnoeic oxygenation (position during preoxygenation, rapid sequence induction applied)
- Fraction of expired O₂ (FeO₂) at the end of preoxygenation
- Application of any apnoeic oxygenation method
- Application of rapid sequence induction intubation
- Drugs used for induction (molecules and doses)
- Elective method for advanced airway management
- Operator's characteristics
- Method used for the second (and following) attempt
- Method used for adequate tube placement confirmation
- Duration of airway management procedure
- Outcome of endotracheal intubation (total number of attempts, laryngoscopic view, minimum SpO₂ during laryngoscopy, need for LMA)
- Advanced airway management-related complications (severe cardiovascular collapse, severe and mild hypoxemia, cardiac arrest, airway injury or any bleeding, aspiration of gastric contents, dental injury, emergency front of neck airway (FONA), cannot intubate cannot oxygenate scenario (CICO), unplanned need for ICU secondary to airway management complications)
- Extubation procedure
- In-hospital mortality

Local investigators are expected to transfer all collected data into an electronic CRF (eCRF, Research Electronic Data Capture – RedCap). Each local investigator will be trained on how to use the eCRF and will receive a personalized username and password. Each patient will be coded through a patient identification number generated by the eCRF and no patient names or initials will be present on the paper CRF.

Data will be handled confidentially and the paper CRF will be stored behind a lock at each local site. Any source of information which may allow to link a record with a patient will be destroyed at the end of the monitoring phase.

STATISTICAL ANALYSIS

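### Airway injury is defined through tracheal intubation alone, so a patient managed only with a supraglottic device cannot have this secondary outcome and the whole-cohort rate is biased low

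*Protocol*

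**What the plan says.** The inclusion criteria (Protocol, Population) cover procedures that need advanced airway management, "either tracheal intubation or SGA placement". Appendix 1 defines advanced airway management in the same way: "The use of either a supraglottic airway device or tracheal intubation as airway management method to provide general anesthesia".

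Airway injury and oral aspiration of gastric contents are listed under Secondary Outcomes as minor adverse events, with no restriction to intubated patients. The Data Collection section gathers both under a heading for complications of advanced airway management, which is neutral as to device.

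The Appendix 1 definitions differ in scope:

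- Airway injury: "Any detectable and clinically relevant injury attributable to tracheal intubation procedure".
- Aspiration: "Presence of vomit at the glottic inlet visualised during airway management in a previously clear airway".
- Dental trauma: "Fracture or avulsion of tooth during airway management".
- Attempt: "Each time a device (SGA, laryngoscope, fiberscope) is introduced in patient's mouth/nose".

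**The concern.** The study population and the airway injury definition do not match. An injury caused by placing an SGA is not attributable to tracheal intubation, so an observer who follows Appendix 1 must leave it out. An observer who follows the Data Collection heading would record it. Dental trauma and attempt are worded to cover any device, and no reason is given for treating injury differently, so this looks like a drafting leftover.

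What is at stake is the rate of one listed secondary outcome, and its consistency across the 210 planned centres. Later analysis cannot repair it. Data are recorded in real time, and anything that links a record to a patient is destroyed at the end of the monitoring phase. Events left out under the definition cannot be recovered after that.

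**Working it through.** **The plan's own figure.** The only related number is the sample size. 1,000 events / 0.10 = 10,000 patients; 10,000 × 1.05 = 10,500; 10,500 / 50 = 210 centres. It reproduces. It rests on the primary composite, which does not include airway injury or aspiration, so nothing below changes it.

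**Airway injury: inputs.** The protocol gives no share of SGA patients and no injury rate by device. Both inputs are therefore assumptions:

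- s = share of patients managed only with an SGA, varied from 10% to 50%
- r = injury risk with an SGA relative to intubation, varied from 0.25 to 1

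**Formula.** Let p be the injury rate in intubated patients.

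- True pooled rate = p·[(1−s) + s·r]
- Rate counted under the literal definition, all patients in the denominator = p·(1−s)
- Share of true injuries missed = s·r / [(1−s) + s·r]

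The rate p cancels, so no absolute injury rate has to be assumed.

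| s | r = 0.25 | r = 0.5 | r = 1 |
|---|---|---|---|
| 10% | 2.7% | 5.3% | 10.0% |
| 20% | 5.9% | 11.1% | 20.0% |
| 30% | 9.7% | 17.6% | 30.0% |
| 40% | 14.3% | 25.0% | 40.0% |
| 50% | 20.0% | 33.3% | 50.0% |

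Example: s = 0.4, r = 0.25 gives 0.10 / (0.60 + 0.10) = 14.3%.

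**Aspiration.** This definition refers to airway management, not to intubation. An SGA patient whose glottic inlet is seen can qualify, so detection is reduced, not excluded. Let v be the fraction of SGA aspirations that are seen there. With equal risk by device, the share missed is s·(1−v). For s = 20–40% this is 20–40% at v = 0 and 10–20% at v = 0.5. The value of v is also an assumption.

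**The case against.** The strongest case on the other side is that the mismatch is one phrase in one minor-event definition, and that the protocol already limits the loss. Clinically relevant bleeding and dental injury are separate secondary outcomes whose definitions do not mention intubation. An SGA patient who also has an intubation attempt can meet the injury definition. No denominator is stated, and a rate among intubated patients only would not be diluted. All of this stands, and it limits the size. It does not remove the point: SGA injury that is neither dental nor counted as bleeding is still lost, and the outcome as listed has no intubated-only restriction.

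A reader might infer more than the documents support:

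- **That aspiration is near zero by definition in SGA patients.** The wording does not say so. That SGA placement usually gives no glottic view is a clinical assumption which the protocol does not state.
- **That hypoxia, and so the primary outcome, is not properly measured in SGA patients,** because the lowest SpO₂ named in Data Collection is tied to laryngoscopy in the entry beginning "Outcome of endotracheal intubation (total number of attempts, laryngoscopic view". That section lists categories of data and is not the case report form, which is not shown. It also lists patient parameters, and hypoxemia as a complication under the device-neutral heading. Severe hypoxia is itself defined without reference to device.
- **That a planned comparison will falsely favour the SGA.** The planned secondary analyses cover place, surgery type, urgency, hypnotic, difficulty, ASA class and BMI, not device.

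**Conclusion.** The airway injury definition is wrong as written for this cohort. Taken literally, it excludes every patient managed only with an SGA from a secondary outcome listed for all patients, and the pooled rate is biased downward. The direction is certain if the definition is followed, SGA patients stay in the denominator and they have any such injuries. The size is not known. For an SGA-only share of 20–40%, about 6–14% of true injuries are missed at a relative risk of 0.25 and 20–40% at equal risk. The higher range should not be read as the estimate: it needs equal risk by device and no SGA injury counted at all.

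The aspiration point is weaker. Detection is probably lower in SGA patients, but this rests on clinical judgement and not on the text. The primary composite and the sample size are unaffected.

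**What to change.** In Appendix 1, make airway injury attributable to advanced airway management (tracheal intubation, SGA placement or rescue technique). Report the rate by device, each with its matching denominator, alongside the pooled rate.

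For aspiration, keep the present definition and add a criterion that needs no glottic view, such as gastric contents seen in the lumen of the SGA or tube. Report it separately, so that the present outcome stays comparable. Counting any gastric contents in the pharynx would go too far, because it would bring in regurgitation and change what the outcome means.

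The cost is one phrase, one added criterion with its data item, and a short note to centres. Minor-event rates will be slightly higher and somewhat less comparable with intubation-only cohorts. The sample size does not change.

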APPENDIX 2 - DETAILED DESCRIPTION OF MEASUREMENTS.

Blood pressure monitoring

Blood pressure monitoring is a standard of care during airway management. Either noninvasive or invasive blood pressure monitoring is required for enrolled patients.

Noninvasive blood pressure monitoring

In case of noninvasive blood pressure monitoring, an appropriate size cuff (relative to the patient's arm circumference) is wrapped around the upper arm of the patient and the interval is set up according to clinical practice.

For the purposes of the current study, the hypotensive event (i.e. SAP < 90 mmHg) should be observed in at least two consecutive measurements.

In case of placement of an arterial line and invasive blood pressure monitoring start by 30 minutes following induction, the reference monitoring method for study outcome identification is the noninvasive blood pressure in place at the start of the procedure.

Invasive blood pressure monitoring

If an arterial line is already in place before intubation and invasive blood pressure monitoring is the standard of practice for the procedure, arterial pressure values from invasive monitoring must be registered and reported in the case report form.

For the purposes of the current study, the hypotensive event (i.e. SAP < 90 mmHg) should be observed in at least two consecutive measurements registered 10 seconds apart.

REFERENCES

- [1] T. G. Weiser *et al.*, "An estimation of the global volume of surgery: a modelling strategy based on available data," *www.thelancet.com*, vol. 372, p. 139, 2008, doi: 10.1016/S0140.
- [2] T. M. Cook, N. Woodall, and C. Frerk, "Major complications of airway management in the UK: Results of the Fourth National Audit Project of the Royal College of Anaesthetists and the Difficult Airway Society. Part 1: Anaesthesia," *Br. J. Anaesth.*, vol. 106, no. 5, pp. 617–631, 2011, doi: 10.1093/bja/aer058.
- [3] T. M. Cook, "Strategies for the prevention of airway complications a narrative review," *Anaesthesia*, vol. 73, no. 1. Blackwell Publishing Ltd, pp. 93–111, Jan. 01, 2018. doi: 10.1111/anae.14123.
- [4] V. Russotto *et al.*, "Intubation Practices and Adverse Peri-intubation Events in Critically III Patients from 29 Countries," *JAMA J. Am. Med. Assoc.*, vol. 325, no. 12, pp. 1164–1172, Mar. 2021, doi: 10.1001/jama.2021.1727.
